Developing an effective treatment modality to lessen thrombotic risk is imperative for this highly prevalent condition. In this proposal, we seek to begin a line of work to answer the question “Can lifestyle changes effectively mitigate the increased risk of VTE in patients with NASH?” focusing initially on the at-risk population genetically susceptible to advanced disease. We hypothesize that fibrinolysis as measured by PAI-1 will be improved with exercise in patients with NASH. We expect this effect to be determined by changes in body composition as PAI-1 levels are dependent on adiposity.

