1.2 Primary Study Endpoints

The primary outcome of interest is change in fibrinolysis as measured by PAI-1 level immediately following completion of the exercise and nutritional counseling program.

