PAI-1 modulates fibrinolysis and is an independent risk factor for VTE. Decreased fibrinolytic activity is a risk factor for VTE.(62, 63) PAI-1, which is produced by adipose tissue and consequently elevated in obesity and NASH and reduced by weight loss,(64) inhibits breakdown of fibrin based clots through physiologic inhibition of plasminogen activators (e.g. urokinase). Elevated PAI-1 levels lead to longer clot lysis times.(65) Multiple studies have documented PAI-1 to be an independent predictor of PE, DVT and PVT when adjusting extensively for prothrombotic confounders.(65-67) PAI-1 is one of the stronger independent risk factors for PVT [OR 6.4 (95% CI 2.5-16.1)].(66) The 4G/5G PAI-1 polymorphism confers additional risk for VTE.

Moderate-intensity exercise leads to improved fibrinolysis in healthy persons. Exercise has a favorable effect on the coagulation system across all three phases of hemostasis.(68-70) Habitual exercise improves primary hemostasis via endothelial-dependent vasodilation and nitric oxide production leading to less platelet activation and aggregation.(71) Moderate intensity exercise improves hemostasis efficiency by activating fibrinolysis in concert with improving coagulation.(68, 69) Specifically, chronic aerobic based training leads to improved fibrinolytic activity in both healthy subjects and those with

cardiovascular disease. This occurs during exercise and persists at rest.(68, 69, 72-75) Reductions in PAI-1 following aerobic exercise programs lasting 3-8 months range from 23-37%.(72, 74-76) When comparing subjects who are aerobically trained to those who are not, further benefit has been observed in fibrinolytic activity via skeletal muscle tPA efficiency.(73) Patients with higher baseline PAI-1 experience the greatest benefit from exercise through both weight and fat loss.(72, 75, 77)

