7.2 Study Procedures

Subjects will be invited for initial consultation performed by the study PI. This will be completed at the GCRC. If subjects are not currently in the Penn State system, they will be registered prior to this consultation through the Penn State Gastroenterology/Hepatology clinic staff ([name] or [name]). For all individuals who provide signed, informed consent, the following baseline measures will be completed:

- Comprehensive history and physical examination
- Anthropometric assessment [height, weight, BMI calculation]
- Physical activity questionnaire (IPAQ)
- Urine Pregnancy Test
- Nutrition counseling will be provided by a Registered Dietitian (RD) to promote a hypocaloric, low-fat dietary intake pattern. In the case that Dietitians are unavailable in person, counseling will be completed by phone or video chat using the Penn State Health-branded Zoom. Food Frequency Questionnaire (FFQ) will be used to assess their current dietary practices. Individual caloric needs will be calculated at baseline using the Mifflin St. Jeor equation, providing resting energy expenditure (REE), multiplied by the appropriate activity factor (AF) to yield total energy expenditure (TEE). Adjusted body weight (ABW) will be used when the participant's BMI is equal to or greater than 30. Five-hundred to 750 calories will be subtracted to promote an approximate weight loss of 1 pound per week for participants whose BMI classifies as overweight or obese. Macronutrient distribution will be recommended at 50-60% carbohydrate, 15-20% protein, and 20-30% fat with <10% total calories attributable to saturated fat. A sodium intake of <2,000 mg daily will be encouraged.

ABW & IBW Calculations:

- Use ABW to calculate REE when BMI ≥ 30
 - ABW calculation:
 - Males: $IBW + 0.38 \times (BW - IBW)$
 - Females: $IBW + 0.32 \times (BW - IBW)$
 - IBW calculation:
 - Males = $106 + 6 \times (Ht.(in)-60)$
 - Females = $100 + 5 \times (Ht.(in)-60)$

REE via Mifflin St. Jeor Equation:

- Male: $10(wt. (kg)) + 6.25(ht. (cm)) - 5(age (yr)) + 5 = REE \times AF = TEE$
- Female: $10(wt. (kg)) + 6.25(ht. (cm)) - 5(age (yr)) - 161 = REE \times AF = TEE$

| Activity Factors: | |
|--|--|
| Lifestyle and Physical Activity Level (PAL) | |

| | |
|--|---------------------|
| Seated work with no option of moving around and little or no strenuous leisure activity | 1.4-1.5 |

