Exercise Medicine Unit or the Hershey Center for Applied Research. Aerobic exercise can be completed on either the treadmill, exercise bike, rowing machine or the elliptical machine. Subjects will be given the opportunity to complete these supervised sessions virtually or in-person as described above. If the subject chooses to complete the strength training sessions virtually, the study EP will schedule and complete exercise sessions using Penn State HIPAA complaint Zoom. Additional home exercise beyond the recommended sessions will be assessed by downloading data from the Fitbit Charge2. Review of downloaded information will take place once a week. Any subject who performs <3 sessions in any given week during the 16-week study period will be required to extend their training by two additional weeks to offset loss of physical conditioning. They can be extended no longer than 4 weeks. If subject misses more than 2 weeks of exercise sessions, they will be discontinued from the study.

Weekly review of dietary logs obtained via self-report through the FitBit application and secure web-based platform with directed feedback by trained study personnel (nutritionist) will also be provided either in-person, telephone interview or video chat. Additionally, participants will be given dietary education forms. In the event that the subject does not self-report their dietary intake through the FitBit platform, the 24-hour dietary recall data collection form will be utilized.

Study investigators will perform an interim history and physical examination on a monthly basis during the exercise protocol. If subject is required to extend protocol, interim history and physical examinations will continued to be performed on a monthly basis. The subject may complete these either in person or virtually.

The purpose of the post-exercise program liver biopsy is to observe changes in stage of fibrosis and NASH Activity Score. Liver biopsy is the gold standard to stage chronic liver disease from NASH and the benefit of disease staging and prognostication outweighs the small risk to the subject. Non-invasive methods of diseases staging (serologic scoring systems NFS, FIB-4) and ultrasound with elastography have inferior performance characteristics with much lower sensitivity and specificity and are hindered by significant inaccuracy with misclassification bias observed in upwards of 25%.(1, 93) Sub-

[REDACTED]

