Control condition (standard of care). Subjects in the control condition will be instructed to continue their medical care at the discretion of their treating medical professional. They will be informed to maintain their current physical activity level. They will be given information from the American Liver Foundation to provide a basic understanding of NASH and to reinforce the counseling from their treating medical professional. We expect this information may result in a subject choosing to exercise, however, similar information-only interventions have led to only small effects, which are accounted for in the sample size calculation. Weekly phone calls will be performed by study personnel to ensure adherence to the protocol (no changes in activity). Subjects will report to Penn State on a monthly basis for anthropometric assessment in the GCRC to confirm their self-reports and study investigators will perform an interim history and physical examination at that time. Subjects may choose to complete this visit in person or virtually using Zoom. Subjects will also be given a Fitbit Charge2HR and downloaded data review will be performed monthly at study visits. These methods of compliance have previously been validated.(91)

This study will be a delayed treatment trial. Subjects randomized to the control condition will be given five months of fitness center membership to UFC and access to an ACSM certified fitness professional for training sessions following completion of the study protocol.

Penn State PM&R Research Laboratories: Housed at Hershey Center for Applied Research (HCAR), the 4,500 ft² facility is comprised of Exercise, Body Composition, Locomotor Training and Gait Laboratories

(Director-[name], collaborator). While the available exercise and body composition assessment equipment totals well over \$1,000,000 and includes multiple gait training devices, this study will utilize the following exercise equipment: Cosmed® K4B2 Portable Metabolic Device and ECG Telemetry system, ParvoMedics TrueMax® 2400 Metabolic Measurement System, and Quinton Q710 Stress Testing/Resting ECG System. Body composition resources include Lunar iDXA® DXA scanner, skinfold and anthropometric calipers.

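### As written, the trial compares supervised exercise plus weekly nutritionist feedback with control, so a PAI-1 difference cannot be attributed to exercise alone

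*Combined protocol and SAP*

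**What the plan says.** Section 7.2 describes dietary support in three places.

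- **Baseline, all consented subjects.** "Nutrition counseling will be provided by a Registered Dietitian (RD) to promote a hypocaloric, low-fat dietary intake pattern". The calorie deficit, with a goal of about one pound per week for overweight or obese participants, is set here.
- **After randomization, before the arms are described.** Participants keep a daily food diary in the Fitbit app and are told how closely their intake met their goals. No arm is named.
- **Under the heading for moderate intensity aerobic exercise.** Dietary logs are reviewed weekly, "with directed feedback by trained study personnel (nutritionist) will also be provided either in-person, telephone interview or video chat". The text continues: "Additionally, participants will be given dietary education forms".

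The control paragraph begins: "Subjects in the control condition will be instructed to continue their medical care at the discretion of their treating medical professional". It adds liver foundation information, a Fitbit, monthly visits and a weekly call whose stated purpose is activity: "Weekly phone calls will be performed by study personnel to ensure adherence to the protocol (no changes in activity". It mentions no dietary review and no nutritionist.

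The plan names the intervention in two ways. Section 1.2 measures PAI-1 "immediately following completion of the exercise and nutritional counseling program". Section 1.1 says: "We hypothesize that fibrinolysis as measured by PAI-1 will be improved with exercise in patients with NASH". Section 7.1 gives the trial's purpose as the efficacy of supervised exercise, and 8.2 credits the exercise intervention with a 23% reduction (9 ng/mL) and expects no change in controls. Section 2.1 describes PAI-1 as "consequently elevated in obesity and NASH and reduced by weight loss".

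**The concern.** A two-arm trial estimates the effect of everything that differs between the arms by design. Here two things differ on the page: supervised exercise, and continuing professional feedback on diet. By the plan's own account the second can move PAI-1 through weight loss. A significant result would show that the package lowers PAI-1. It would not show that exercise does, which is what 1.1 hypothesizes and what 7.1 says the trial is for.

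The analysis plan cannot separate the two. Section 8.3 says only that multivariable regression models will be built and names no dietary or weight covariate. Adjusting for weight change after randomization would not isolate exercise either, because 1.1 expects the exercise effect itself to run through body composition.

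**Working it through.** **1. What differs between the arms, from section 7.2 and its schedule**

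| Element | Exercise | Control |
|---|---|---|
| Baseline dietitian counseling and calorie goal | yes | yes |
| Food diary with information on meeting goals | yes (no arm named) | yes (no arm named) |
| Weekly log review with nutritionist feedback | yes | not described |
| Dietary education forms | yes | not described |
| Weekly study contact | supervised sessions, dietary feedback | call about activity |

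The schedule lists a weekly dietary log in a column shared by exercise and control. It lists the log, not the feedback. The same column shows weekly Fitbit downloads, whereas the control paragraph says monthly review, so the column is not a reliable guide to what each arm receives. The control paragraph does repeat other shared items (Fitbit, monthly history and examination), which gives its silence on dietary feedback some weight.

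**2. The plan's own power figure**

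Inputs from 8.2: difference 9 ng/mL, SDs 14.0 (exercise) and 2.0 (control), two-sided alpha 0.05, unequal-variance t-test, 2:1 allocation. With v1 = 14²/n1 and v2 = 2²/n2, SE = √(v1 + v2), df = (v1 + v2)² / [v1²/(n1−1) + v2²/(n2−1)], and power comes from the noncentral t with noncentrality 9/SE.

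At 22:11: v1 = 8.909, v2 = 0.364, SE = 3.045, df = 22.7, noncentrality = 2.956, power = 80.74%. This is the printed figure. It corresponds to 33 evaluable subjects (33/0.80 = 41.25, rounded up to 42). With 28:14 evaluable the power is 89.7%. That mismatch is a separate matter. 22:11 is used below because it reproduces the plan.

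**3. What a dietary share would mean (assumed, not estimated)**

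The documents give no effect of the weekly feedback on PAI-1. Suppose the total difference is 9 ng/mL and the feedback supplies 10%, 25% or 50% of it. At 22:11:

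| Assumed dietary share | Exercise part | Power for the exercise part alone | Chance of a significant result if exercise did nothing and the dietary part were real |
|---|---|---|---|
| 10% (0.9 ng/mL) | 8.1 | 72% | 5.9% |
| 25% (2.25 ng/mL) | 6.75 | 56% | 10.9% |
| 50% (4.5 ng/mL) | 4.5 | 29% | 29.3% |

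The last column is not an error rate for the package test, since a package effect would then exist. It is the chance of crediting exercise with an effect that it did not have.

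**The case against.** The best reply is that the asymmetry is not certain. The sentences on dietary feedback speak of participants and subjects without naming an arm, and the schedule column is shared. If controls are meant to receive the feedback, there is no confounding and only the control paragraph is incomplete. This stands as a reason to ask. As printed, however, the feedback lies between rules for exercise sessions and monthly examinations during the exercise protocol, and nothing assigns it to controls.

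It can also be said that the plan already presents a package: 1.1 asks about lifestyle changes, 7.1 opens with lifestyle interventions, and 1.2 names counseling. That is partly true and is why the repair is small. The same sections then credit exercise specifically, so the wording is mixed.

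A reader might go further in three ways that the documents do not support:

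- **That diet as a whole is confounded with exercise.** Baseline counseling and the food diary with information on goals appear common to both arms.
- **That the one-pound-per-week goal, 16 to 20 lb over 16 to 20 weeks, measures the bias.** The goal is set at baseline for eligible subjects in both arms, so it is not a between-arm difference.
- **That a given number of ng/mL belongs to diet.** No figure in the documents anchors such a share.

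**Conclusion.** The concern holds in limited form. As written, the randomized contrast is supervised exercise plus weekly nutritionist feedback and education forms versus control. The comparison of that package with control is valid, and the power calculation is not altered. What fails is attribution to exercise alone, as 1.1, 7.1 and 8.2 have it.

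The size of the misattribution cannot be stated from the documents; the shares in the working are assumptions that show direction and sensitivity only. The verdict rests on reading the feedback paragraph as belonging to the heading it stands under. If both arms receive the feedback, the concern falls away.

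**What to change.** Restate the hypothesis in 1.1, the aim in 7.1, the sample-size rationale in 8.2 and the planned conclusion as supervised exercise plus weekly nutritional counseling versus control, matching 1.2. In 8.2, add that the 9 ng/mL is based on studies of exercise regimens and is being used for the package. State that a difference will not be attributed to exercise alone. The cost is wording, and a narrower claim about exercise itself.

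If controls are in fact meant to receive the same weekly feedback, reconcile the control paragraph and the schedule with the exercise-arm text so that all three say so; no restatement is then needed for this reason.

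Newly extending the feedback to controls would be a different decision and not a free one. It needs nutritionist time and log review beyond the activity call now planned. If the 9 ng/mL is the total package effect and, purely as an assumption, 1 to 3 ng/mL of it came from the feedback, the remaining 8 to 6 ng/mL would have 71% to 47% power at 22:11, against 80.7% now. If the 9 ng/mL is the effect of exercise alone, as 8.2 reads, that loss would not arise.

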Penn State University Fitness Center: Housed with the Penn State University Conference Center, the University Fitness Center has a plethora of resources including free weights and cardiovascular equipment necessary for this protocol. In addition, group fitness classes, gymnasium, locker room and shower facilities are available during convenient all-day hours, 7 days a week. In addition to the dedicated NASHFit exercise physiologist, there are an additional seven exercise physiologists on staff. There are private rooms available for study visits allowing for completion of assessment immediately before or after an exercise session by trained study personnel.

Follow-up. Subjects will be seen by a study investigator immediately after the completion of the 16-week exercise intervention. This will be completed at the Penn State Hershey GCRC and the PM&R research laboratory. A focused history and physical exam, anthropometric assessment including DXA scan, IPAQ, dietary log, cardiopulmonary fitness testing, laboratories, stool sample, MRI-PDFF, PROMIS and end of study survey will be completed. A sub-study of ten subjects will be required to complete a liver biopsy following sub-randomization at the completion of the exercise intervention. Samples collected for research purposes will be stored per standard SOP requirements of the Pathology Department. Subjects will be compensated (\$25 at baseline, \$25 at completion of the exercise regimen, \$100 following liver biopsy obtained at the completion of the exercise regimen if selected). They will also be allowed to keep their FitBit Charge2 HR. Finally, participants will receive a list of local fitness facilities available in the area. Twelve weeks after the end of the program, study staff will contact participants in the exercise arm by phone to complete a follow up questionnaire.

Paired liver biopsy samples (enrollment sample and post-exercise sub randomized sample) will be sent to a biotechnology company, Reveal Biosciences, to undergo an automated computerized ImageDx analysis to evaluate the severity of NASH. Samples will be shipped directly from the Pathology (where they are stored) and they will be de-identified.

Schedule of visits and study protocol assessments

| Visit | Initial Assessment | Exercise Instruction | Exercise Program or Control | End of exercise program |
|---|--------------------|----------------------|-----------------------------|-------------------------|

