10.0 Data and Safety Monitoring Plan

10.1 Periodic evaluation of data
[name] (hepatology) will serve as the independent medical monitor for the proposed research project and will meet with [name] bi-annually. Under the mentorship of [name], [name] will provide oversight for the conduct of the study and collectively we will follow the protocol proposed and ensure all eligibility criteria and consent requirements are met prior to enrolling a subject. All study

procedures and adverse event (AE) reporting will occur in accordance with the Penn State College of Medicine IRB approved protocol. These monitoring activities will remain in place until all participants have completed the intervention. [name] will review AEs on a rolling basis and quarterly. He will review study enrollment and any early termination of a subject's participation. Any issues requiring study modification or a change in the risk/benefit to a subject will be reported immediately to the IRB. A summary of AEs, study progress and protocol modifications will be sent to the IRB for review in the annual continuing review report.

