10.3 Method of collection of safety information

Case report forms will be utilized for AEs. Study visits will assess for AEs.

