10.7 Statistical tests

Subjects will be compared in their randomized groups according to SAE occurrence. Chi-squared and Fisher's exact test will be used to analyze our categorical endpoints. A p value of <0.05 will be significant. Intention to treat analysis will be performed. Analyses will be conducted using SAS version 9.4.

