11.0 Risks

This study is designed to assess the efficacy of exercise in patients with NASH. The main risks of any exercise protocol include physical injury (e.g. musculoskeletal), or an adverse cardiovascular event (myocardial infarction). All exercise sessions will be monitored by ACSM certified fitness professionals and an available physician will be available should any injury or cardiovascular event occur. In addition, there are several other risks related to the measures of secondary outcomes:

MRI scan:

- Discomfort related to claustrophobia from being inside an enclosed space for the MRI scan and loud banging noise during the study for which temporary hearing loss has been reported (wearing earplugs can help prevent this).

DXA scan:

- Radiation exposure from the DXA scan that is being used to determine body composition

Venipuncture (blood draw):

- Discomfort associated with removing blood by venipuncture (by needle from a vein) including mild discomfort and/or a black and blue mark at the site of puncture.
- Less common risks of venipuncture include a small blood clot, infection or bleeding at the puncture site, and on rare occasions fainting during the procedure.

Cardiopulmonary Testing:

- Maximal oxygen uptake testing involves exercising to exhaustion. Side effects may include, fainting, chest pains, weakness, vomiting, muscle soreness and headache.
- Risk of falling due to increasing speed and incline of the treadmill during exhaustive exercise.

Liver biopsy:(95)

- 5-20% musculoskeletal pain despite topical and deep anesthetic
- <1% risk of
 - Major bleeding
 - Infection
 - <Inadvertent organ puncture (e.g. kidney, lung, gallbladder, colon)

There is also an inherent risk in randomization as subjects are assigned to a study group by chance. The study program a subject is assigned to may prove to be less effective or have more side effects than the other study groups.

Incidental findings discovered through history & physical exam, pregnancy testing, blood draws, cardiopulmonary testing, imaging (MRI and DXA) and during the exercise protocol will be handled on an individual basis according to standard medical practice at the discretion of the study PI. These results will be communicated to not only the subject but also the subject's primary care physician and/or the appropriate medical specialist best suited for further evaluation.

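### The between-arm SAE comparison has no common window or common method of asking, although staff contact is more frequent and can last longer in the exercise arm, so it may be biased

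*Combined protocol and SAP*

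**What the plan says.** **Comparison.** Section 10.7: "Subjects will be compared in their randomized groups according to SAE occurrence", and "Chi-squared and Fisher's exact test will be used to analyze our categorical endpoints". No window, person-time or cut-off is attached.

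**How AEs are collected.** Section 10.3 provides case report forms and says "Study visits will assess for AEs". It does not define a study visit or give a script. Section 7.2 gives both arms a monthly history and physical by an investigator, which may be virtual in either arm, and both arms have an end-of-program visit.

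**Contact in the exercise arm only.** Section 7.2 sets supervised sessions five times a week after the lead-in. Section 11.0: "All exercise sessions will be monitored by ACSM certified fitness professionals". Subjects with fewer than three sessions in a week have their training extended (section 7.2): "They can be extended no longer than 4 weeks", with monthly examinations continuing. The follow-up text adds: "Twelve weeks after the end of the program, study staff will contact participants in the exercise arm by phone". Its stated purpose is a questionnaire whose content is not described.

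**Contact in the control arm only.** Section 7.2: "Weekly phone calls will be performed by study personnel to ensure adherence to the protocol (no changes in activity").

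**Duration.** Section 7.3 gives 20 weeks of participation without distinguishing the arms. Section 10.1 says of oversight: "These monitoring activities will remain in place until all participants have completed the intervention".

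**The concern.** A chi-squared or Fisher test on the proportion of subjects with an SAE compares like with like only if both arms are observed for the same time and events have the same chance of being noticed. The plan secures neither. An extended exerciser is examined by investigators beyond the point where a control's follow-up ends, so the window can differ under the plan's own AE route, without relying on the 12-week call. Session staff also see exercisers far more often than anyone sees controls, whose weekly call has a different stated purpose.

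A program with no true excess of harm could then show a higher SAE proportion, and a true excess could not be cleanly separated from the difference in observation. With 42 subjects, a few differentially captured events could change the safety statement.

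**Working it through.** The plan gives no SAE rate, SAE window or power for the harms comparison, so there is no figure to reproduce. The check asks how large the distortion could be.

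**Inputs from the plan.** 28 exercise and 14 control subjects (8.2); 20 weeks of participation (7.3); extension of at most 4 weeks (7.2); call 12 weeks after the program (7.2); two-sided 0.05 (10.7 gives p < 0.05).

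**Assumptions.** The same constant hazard in both arms. The 20-week risk p is taken as 2%, 5%, 10% or 20%, because the plan states none. Controls are observed for 20 weeks.

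**Exercise windows.**
- Every exerciser extended 4 weeks: 20 + 4 = 24 weeks.
- Call counted, no extension: 20 + 12 = 32 weeks.
- A quarter of exercisers extended 4 weeks (the fraction is an assumption): a 1:3 mix of 24 and 20 weeks.

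**Formula.** Risk over W weeks = 1 − (1 − p)^(W/20). Apparent risk ratio = that risk divided by p.

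At p = 10%:
- 24 weeks: 1 − 0.9^1.2 = 0.1188, ratio 1.19.
- A quarter extended: 0.25 × 0.1188 + 0.75 × 0.10 = 0.1047, ratio 1.05.
- 32 weeks: 1 − 0.9^1.6 = 0.1551, ratio 1.55.

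| Assumed 20-week risk | Quarter extended | All extended (24 v 20) | Call counted (32 v 20) |
|---|---|---|---|
| 2% | 1.05 | 1.20 | 1.59 |
| 5% | 1.05 | 1.19 | 1.58 |
| 10% | 1.05 | 1.19 | 1.55 |
| 20% | 1.04 | 1.17 | 1.50 |

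**Test error.** Probability of p < 0.05 in either direction at 28 v 14, summed over all possible tables (chi-squared uncorrected):

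| Risk and test | Equal 20 weeks | Quarter extended | All extended | Call counted |
|---|---|---|---|---|
| 10%, Fisher | 1.9% | 1.8% | 1.5% | 1.9% |
| 10%, chi-squared | 3.6% | 3.3% | 2.9% | 4.0% |
| 20%, Fisher | 2.9% | 2.8% | 3.2% | 7.3% |
| 20%, chi-squared | 4.6% | 4.7% | 5.3% | 10.2% |

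Totals hide direction. At 10% risk with the call counted, rejections against exercise rise from 0.1% to 1.4% (Fisher) and from 0.4% to 3.3% (chi-squared). With all exercisers extended and no call, they rise from 0.1% to 0.3% and from 0.4% to 1.0%.

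The last two columns of each table are upper bounds for their scenarios. The first of these extends every exerciser, whereas only those with missed sessions are extended. The second assumes that the call captures every SAE in the 12 weeks before it. The effect of more frequent contact within the 20 weeks cannot be computed, because the plan gives nothing on detection rates.

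**The case against.** The strongest case against is that the plan names one AE route, study visits, and that the investigator examinations on this route are monthly in both arms. Supervision of sessions is described as instruction and safety cover, and nothing says that AEs are recorded there. The 12-week questionnaire is not said to ask about harms. Section 7.3 gives one duration for everyone. SAEs also depend less on contact frequency than minor events do.

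Much of this stands. A reader might infer that harms are sought at every session and on the call, but the documents do not say so. A reader might also take the sentence in 10.1 on how long monitoring lasts as bringing the call into the comparison. That sentence concerns trial-level oversight and does not define a per-subject window. Nor does the suspension rule in 10.8 add to the point: it is the medical monitor's judgement against expectation and is not described as a comparison of arms.

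Direction is not settled either. Section 7.2 discontinues subjects who miss more than two weeks of exercise sessions, a rule that can apply only to exercisers. Although 3.3.2 says withdrawn subjects are followed at the same time points, its example is a single phone call. This could lower ascertainment in the exercise arm.

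The objection does not remove the gap. Section 7.3 is a length of participation that the extension and the call already exceed, so it cannot settle which events count. The extension, with its continuing examinations, has no control counterpart. Uncertainty about direction is itself a reason to fix the window.

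**Conclusion.** The point holds as a risk of bias from an undefined window and unequal contact, most likely towards more events in the exercise arm. It does not hold as an established bias against exercise, which a reader might infer from the contact schedule.

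Its demonstrable size is modest. From the extension alone, the apparent risk ratio is at most about 1.2 if all exercisers are extended by 4 weeks, and about 1.05 if a quarter are, with little effect on test error. Ratios of 1.5 to 1.6, and false-positive rates of 10.2% (chi-squared) or 7.3% (Fisher) at a 20% event risk, apply only if the 12-week call elicits SAEs and those events enter the comparison. The documents state neither. All figures rest on assumed event rates and an equal constant hazard.

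The change is worth making because it is cheap and removes the ambiguity before any events are seen.

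**What to change.** **Section 10.7.** Limit the between-arm SAE comparison to events with onset from randomization to 20 weeks after randomization in both arms, whatever the extension. List later events separately: those in extension weeks beyond week 20, those reported at the 12-week call, and those arising from the end-of-program biopsy.

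**Section 10.3.** Ask the same scripted AE question at the weekly contact that each arm already has (dietary and Fitbit review for exercise, phone call for control) and at the monthly history and physical in both arms.

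**Events first noted at a session.** Keep every in-window SAE in the comparison however it was detected. Flag those first noted at a supervised session, and show a sensitivity analysis without them. Removing them from the main comparison would hide on-treatment harms of the kind section 11.0 names as the main risks.

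**Cost.** A few sentences in 10.3 and 10.7 and one question at existing contacts, with no new visits. The small downside is that late exercise-arm events are reported descriptively and not tested. With equal hazard and equal ascertainment, the common window brings the expected risk ratio back to 1.00.
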